Acoustic Radiation Force Impulse (ARFI) Imaging for Targeted Prostate Biopsy

Document Date: October 18, 2023

NCT04607135

Purpose of the Study

The objective of the proposed study is to evaluate the feasibility of a new ultrasonic acoustic radiation force impulse (ARFI) elasticity imaging system with a custom-designed transducer and biopsy guide to provide imaging guidance and targeting during prostate needle biopsy. This study will be conducted in two parts. Part 1 will evaluate a new, custom designed ultrasound transducer and needle guide in performing systematic transrectal ultrasound-guided prostate biopsies, as is the current standard-of-care. In addition to standard imaging, the new probe will be capable of ARFI measurements of tissue stiffness. Part 2 will evaluate the feasibility of targeted prostate biopsy guidance using ultrasound ARFI targeting as compared to ultrasound-MR fusion targeting in subjects electing to have ultrasound fusion-MR targeted biopsy procedures.

Background & Significance

Prostate cancer is the most common cancer and the second leading cause of cancer death for American men. For men harboring occult aggressive cancers, early diagnosis is essential for better treatment and increasing survival rate. Although the current screening techniques (prostate-specific antigen (PSA) blood testing and digital rectal examination (DRE)) are moderately sensitive but lack specificity for cancer screening, resulting diagnostic biopsies have significant shortcomings. Transrectal ultrasound is currently used to provide biopsy guidance only; however, it has poor sensitivity and specificity for prostate cancer. Without a good imaging technique to guide the needle biopsy in prostate glands, only about 25% of tests are positive for cancer in more than 1 million prostate biopsies performed each year; the false negative rates range from 25-45% based on the first-time biopsy. Although studies have shown more biopsy cores can increase diagnostic accuracy, prostate needle biopsy is an invasive procedure for the patient associated with both pain and risks, such as infection, hematuria (blood in the urine), urinary retention, hematochezia (blood during bowel movement), and hematospermia (blood in the semen). More biopsy cores mean higher risk for the patient. Thus, improved needle biopsy procedures guided by ARFI imaging would be of great clinical benefit.

Design & Procedures

PART 1: The new ultrasound probe will be used in the same manner as current probes for standard-of-care prostate biopsy using systematic sampling with transrectal ultrasound (TRUS) guidance. In addition to B-mode images during the procedure, ARFI images will be acquired immediately before each needle insertion, after needle insertion, and following needle removal in each sampled image plane. The additional time required for ARFI measurements will be approximately 5-10 minutes.

PART 2: Three-dimensional ARFI images of the prostate will be acquired by sweeping the imaging plane through the prostate volume as in our current study of ARFI prostate imaging (Pro00006458), using the custom-designed ARFI-capable ultrasound probes. Image volume acquisition will take approximately 12 minutes, and not more than 20 minutes. Display of these images will be in real-time, and immediately following the volume acquisition, the most suspicious targets (up to 3) in the gland will be identified. The ultrasound probe will be positioned to image the target in plane and two-four biopsy cores will be acquired per target – with ARFI and B-mode image data acquired from each targeting procedure. The

ARFI ultrasound probe will be removed, and the standard ultrasound-MR fusion biopsy procedure will then proceed using the clinical ultrasound fusion-MR system. The additional time required to acquire the ARFI image volume and perform the ARFI-targeted biopsy cores is approximately 25-30 minutes

Selection of Subjects

PART 1: We will enroll patients scheduled for standard TRUS biopsy with suspected PCa.

PART 2: We will enroll patients with suspected PCa who are scheduled to undergo an ultrasound fusion-MR prostate biopsy.

Due to the nature of PCa, this study is open to men only; women and children are excluded. It is open to members of all racial and ethnic groups. Patients will be recruited by the treating physician or a healthcare provider known to the patient at the time of consultation.

Inclusion criteria:

PART 1: Men with suspected PCa based on suspicious PSA or DRE, or abnormal radiological finding scheduled for standard TRUS prostate biopsy;

PART 2: Men who are scheduled to undergo ultrasound fusion-MR prostate biopsy;

Men who are willing to participate in the study;

Subjects must freely sign informed consent to enroll in the study;

18 years or older

Assessing eligibility: eligibility for the study will be assessed, based upon the above criteria, by the participating urologist at the time of consultation.

Exclusion criteria:

Men who have had previous treatment for PCa including radiation, cryoablation, chemotherapy, surgery, high intensity focused ultrasound (HIFU), laser therapy or hormone therapy;

Men who have had previous non-pharmacological invasive or minimally invasive treatment for benign prostatic hypertrophy (BPH) (i.e., TURP, TUMPT, WIT, TUNA, etc); standard pharmacological treatment of BPH is allowable;

Men who are mentally impaired and cannot give written consent;

Men with anomalies of the rectum

Subject Recruitment and Compensation

This study will be open to members of all demographic groups who meet the eligibility criteria. The study will be introduced to potential subjects by a healthcare provider known to them. If interested, someone from the research team will discuss the study with the potential subject. Potential subjects will be identified from the pool of adult male urology patients at clinic 1G, the Duke Cancer Center, the Duke Raleigh Urology clinic or referred from an outside facility which will provide sampling from a diverse

patient population spanning all demographics in order to support equitable subject selection. Subjects will not receive any compensation. We will need to review protected health information such as name, history number, appointment date and physician, past cancer history, other past medical history and other protected health information (PHI) to determine study eligibility. This activity is used only to identify subjects, and information resulting from this activity will be used only to assess eligibility of subject. Once the subject has been assigned to the study and consent has been obtained, documentation of eligibility will be recorded.

PART 1: Ten patients will be recruited for the first part of the study, which will evaluate the performance of a new, custom designed ultrasound probe and biopsy guide for systematic transrectal ultrasound guided prostate biopsies.

PART 2: Up to 60 patients will be recruited per our existing NIH grant.

Study Interventions

PART 1: Participation will not affect the subjects' standard clinical treatment in any way.

PART 2: Two-four additional biopsy cores per target lesion will be acquired at suspicious positions identified by ARFI targeting.

Risk/Benefit Assessment

PART 1: If, as we expect, the B-mode image quality and biopsy guide performance of the new transducer and system are comparable or better than the current clinical TRUS system, there should be no increased risk to the patient from using the prototype system for standard systematic TRUS biopsy. If the imaging capabilities of the new ultrasound probe are insufficient as compared to the clinical ultrasound system, the attending physician will remove the new probe and use the clinical system to perform the required measurements and TRUS-guided biopsy. If necessary, this change would require approximately 5 minutes. Per our current IRB protocol, the additional ARFI images that will be acquired in each image plane where a biopsy is taken are of minimal risk. The primary risk associated with ARFI measurements using the new ultrasound probe is slightly increased tissue heating that is within the FDA limits for ultrasound, and a theoretical risk of cavitation. There will be no direct benefit to the patients enrolled in this part of the study.

PART 2: The primary risk associated with the second part of the study is the acquisition of two-four additional biopsy cores per target as compared to the number obtained during the standard-of-care ultrasound fusion-MR biopsy acquisitions. Actually, subjects may require fewer overall numbers of biopsy cores as abnormal areas of imaging (ARFI and MRI) will be targeted compared to standard, blind, non-targeted prostate biopsy. Per our current IRB protocol (Pro00006458), while minimal, the primary risk associated with ARFI imaging is tissue heating, though temperature increases are below FDA limits for ultrasound measurements. There is also a theoretical risk of acoustic cavitation associated with the ARFI pulses, however, this is unexpected based upon the pulse MI and duration (Nightingale et. al, JUM, 2015), and has not been observed in the over 200 ARFI/SWE imaging studies we have performed to

date. The additional time required for the ARFI measurements and targeted biopsy procedure will extend the time the patient will receive anesthesia. Additionally, this study will require a separate insertion of the ARFI probe in addition to the standard TRUS probe used for MRI targeted biopsy. The subject will benefit directly from the acquisition of two-four additional biopsy cores per ARFI target at suspicious positions identified by ARFI imaging.

We consider the risks identified to be minimal, and we hypothesize that the ARFI technology has significant potential for improving the diagnostic accuracy of TRUS prostate biopsy. Thus, we consider this study to have a favorable benefit/risk ratio.

Data Analysis & Statistical Considerations

For the first part of the study, images acquired with the new ultrasound transducer will be evaluated qualitatively by the attending physician to determine if they are adequate for ultrasonic systematic biopsy sampling of the prostate. ARFI images will also be obtained and will be analyzed off-line using existing methods to assess tissue stiffness, needle visualization, and changes in tissue stiffness following needle removal. We expect b-mode ultrasound imaging and ARFI imaging capabilities to be comparable or superior to those we have obtained with the transducer/system we have been using under our current imaging protocol. We plan to include up to 10 patients in this Part 1 study. We do not plan to perform statistical analyses for this part because our goal is primarily to verify the functionality of the probe/system prior to initiating part 2.

For the second part of the study, we will test the hypothesis that ARFI guided targeted biopsy provides a higher PCa detection rate than that reported for systematic TRUS biopsy. We will also compare ARFI-targeted biopsy performance to that of MR-ultrasound fusion targeting by evaluating the biopsy cores obtained using each method with standard statistical tests to compare the length and grade of cancerous tissue in the cores. Biopsies will be scored for clinically significant disease (CSD) using the same clinical standard as for TRUS biopsy (e.g., percent PCa per/core, Gleason score, Gleason Grade Group) and yield of CSD (i.e., number of cores containing CSD/total number of cores) for each biopsy method. In addition, the spatial location of the targeted cores within the prostate will be compared between ARFI and Ultrasound-MR fusion. Assuming an ARFI imaging specificity for CSD of 70% (our preliminary data from Protocol Pro00006458 in patients receiving radical prostatectomy yielded 79% CSD from ARFI suspicious regions, and, 71% detection of all CSD present in the gland), and comparing to the systematic sampling TRUS PCa mean detection rate of 30% that has been well-established in the literature, inclusion of 35, 45, and 50 patients would achieve study powers of 80%, 90%, and 95%, respectively through a one-mean, one-sample equivalence test with a 30% testing margin and a standard deviation of up to 20% of the target ARFI imaging specificity. We plan to include 50 patients in this Part 2 study, plus 10 initial patients for early phase development and workflow integration (60 total in part 2).

Direct personal identifiers in study records will not be disclosed outside of Duke University Health System. For records disclosed outside of Duke, subjects will be assigned a unique code number.

Data & Safety Monitoring

The Principal Investigator, [name], will be responsible for monitoring the safety of these studies. As previously described, we do not anticipate any adverse events. However, in the event that adverse events occur, they will be immediately reported in detail in writing to the Duke University Medical Center's Institutional Review Board (IRB) in accordance with the re portable events policy.

Data for this study, including relevant medical records such as prostate-specific antigen (PSA) level, biopsy results, and any available imaging studies (MR, prior ultrasound, etc.) will be analyzed at the completion of study enrollment. A code number will be assigned to each subject, which will be used for data analysis and result reporting. The patient name and history number will be recorded only in the electronic enrollment log, which will also have the unique code number. The patient consent forms will be stored in the office of the primary study coordinator, which is locked when the primary study coordinator is not present and is a restricted access area. The protected health information will not be reused or disclosed to any other person or entity, except as required by law, for authorized oversight of the research study.

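### The two Part 2 eligibility statements disagree on suspected cancer, and no rule keeps previously diagnosed cancers out of the detection rate compared with 30%

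*Combined protocol and SAP*

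**What the plan says.** Under Selection of Subjects, the opening statement for Part 2 reads "We will enroll patients with suspected PCa who are scheduled to undergo an ultrasound fusion-MR prostate biopsy". A few lines later, the itemised Part 2 entry under Inclusion criteria reads "PART 2: Men who are scheduled to undergo ultrasound fusion-MR prostate biopsy", with no mention of suspicion. The Part 1 entry in the same list keeps the condition and defines it: "PART 1: Men with suspected PCa based on suspicious PSA or DRE, or abnormal radiological finding scheduled for standard TRUS prostate biopsy".

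The only cancer-related entry under Exclusion criteria is "Men who have had previous treatment for PCa including radiation, cryoablation, chemotherapy, surgery, high intensity focused ultrasound (HIFU), laser therapy or hormone therapy". A prior positive biopsy without treatment is not listed. Under Assessing eligibility, "eligibility for the study will be assessed, based upon the above criteria, by the participating urologist at the time of consultation". Subject Recruitment and Compensation adds that past cancer history is reviewed to determine eligibility and that this information serves eligibility only. It does not say what follows if an untreated cancer is found.

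Data Analysis & Statistical Considerations sets the Part 2 hypothesis: "ARFI guided targeted biopsy provides a higher PCa detection rate than that reported for systematic TRUS biopsy". The comparator is a literature mean of 30%, and 50 men are planned beyond 10 initial development patients. That section does not say whether a cancer known before the study biopsy counts as a detection, and it plans no subgroup or analysis set by prior diagnosis.

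**The concern.** A man with untreated, biopsy-proven cancer who is booked for a repeat fusion biopsy satisfies every itemised inclusion criterion and meets no exclusion. He already has the outcome being counted. A positive ARFI core in him re-finds a known cancer, whereas Background & Significance describes the problem as early diagnosis of occult disease and false negatives at first biopsy.

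At stake is the comparison with 30%. If some of the men are known to have cancer and ARFI is positive in more than 30% of them, the pooled rate exceeds 30% even when ARFI does no better than the benchmark in men who are only under suspicion. This problem is separate from the usual doubts about a historical comparator: it would remain with a literature rate perfectly matched to men with suspected cancer.

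**Working it through.** **1. The eligibility texts side by side (Part 2)**

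| Place | Suspected cancer required? | Prior untreated diagnosis barred? |
|---|---|---|
| Selection of Subjects, opening statement | Yes, undefined | Not stated |
| Inclusion criteria, Part 2 entry | No | No |
| Exclusion criteria | – | No; previous treatment only |

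The first two rows conflict. No row settles the case of the previously diagnosed, untreated man.

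**2. The plan's own figure**

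The plan states 35, 45 and 50 patients for 80%, 90% and 95% power. With mean 0.70, reference 0.30, margin 0.30, SD 0.20 (absolute) and one-sided alpha 0.05 (assumed, as none is stated), the one-sample equivalence formula is n = [SD × (z(1−α) + z(1−β/2)) / (margin − |difference|)]². This gives [0.20 × (1.645 + z(1−β/2)) / (0.30 − 0.40)]² = 35, 44 and 52, close to the stated values. It works only because a negative distance is squared, which is a separate matter. What this point takes from the plan is N = 50 and the 30% reference. Neither depends on who is eligible.

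**3. Effect of mixing in known cancers**

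Inputs from the documents: N = 50 and benchmark 0.30. Assumptions, because the documents are silent:
- f, the share of enrolled men with known untreated cancer: 10% to 40%.
- q, the ARFI-positive rate among them: 0.50 to 0.80. The nearest figure in the plan is 71% detection of all clinically significant disease, in prostatectomy patients.
- True ARFI rate of 0.30 in men without a prior diagnosis, so that any success is false.
- An exact one-sided binomial test of 0.30, with one result per man. The plan names an equivalence test and no alpha.

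Expected pooled rate = f × q + (1 − f) × 0.30. For f = 0.20 and q = 0.50 this is 0.10 + 0.24 = 34%. For f = 0.20 and q = 0.80 it is 0.16 + 0.24 = 40%.

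Cut-offs against 0.30 with 50 men are at least 21 positive (nominal 0.05, actual size 4.8%) and at least 23 positive (nominal 0.025, actual size 1.2%). The false-success chance is the upper tail, at the cut-off, of Binomial(50f, q) + Binomial(50(1 − f), 0.30).

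False-success chance, nominal 0.05 / nominal 0.025:

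| f | q = 0.50 | q = 0.70 | q = 0.80 |
|---|---|---|---|
| 0 | 4.8% / 1.2% | 4.8% / 1.2% | 4.8% / 1.2% |
| 10% | 8.6% / 2.6% | 14.0% / 4.7% | 17% / 6% |
| 20% | 14.5% / 5.0% | 31.8% / 14.0% | 43% / 21% |
| 30% | 22.5% / 9.0% | 55.8% / 31.9% | 74% / 50% |
| 40% | 32.5% / 14.9% | 78.0% / 56.0% | 93% / 79% |

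The direction is the same in every cell with f above zero. The size varies roughly tenfold at nominal 0.05 and thirtyfold at nominal 0.025.

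**The case against.** The strongest reply is that the section should be read as a whole. The reference under Assessing eligibility to the criteria above comes after both the selection statement and the itemised list, so the urologist may apply both. Known-cancer men would then arguably never enter. This stands to the extent that eligibility is contradictory and not settled. It does not remove the problem, because suspicion is undefined for Part 2, and even the fuller Part 1 wording does not expressly bar a man with a prior positive biopsy.

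A reader might infer that the plan makes known-cancer men eligible and counts their cancers as ARFI detections. The documents do not support that. One of the two statements points the other way, and the counting is an inference from silence. The statistical section also moves between cancer detection, clinically significant disease and a per-core yield. If success means clinically significant disease, re-finding a known insignificant cancer would not count.

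A reader might also treat such men as near-certain successes. That is unsupported too: ARFI must still pick the lesion, with up to three targets, and two to four cores per target must hit it. Hence the range for q. The binomial test is also an assumption, so the percentages illustrate the effect and are not operating characteristics of the planned test.

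Finally, the reach is limited. The within-man comparison of ARFI with MR-fusion targeting, which Purpose of the Study presents as the Part 2 aim, does not use the 30% figure and is not exposed to this mismatch.

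**Conclusion.** The concern holds as a contradiction with a consequence. The two Part 2 statements differ on suspected cancer, the exclusions reach only treated cancer, and no rule keeps a previously diagnosed cancer out of the rate compared with 30%. If the itemised list is followed, the bias favours ARFI whenever positivity among known-cancer men exceeds 30%.

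The amount cannot be computed from the documents. Over the assumed ranges it runs from modest (8.6% against 4.8%, or 2.6% against 1.2%) to severe (93%, or 79%). Confidence is high on the wording conflict and the direction of the bias, and low on its size. It should be corrected before the data are analysed, which Data & Safety Monitoring places at the completion of enrolment.

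**What to change.** 1. Reconcile the two Part 2 statements by carrying the suspected-cancer condition into the itemised inclusion criterion, with its basis defined as it is for Part 1.
2. State whether men with previously diagnosed, untreated cancer are eligible. Restoring the suspicion wording does not settle this alone.
3. If any such men are or have been enrolled, keep them in the within-man ARFI versus MR-fusion comparison. Restrict the detection rate compared with 30% to men without a prior prostate cancer diagnosis, and say so in the statistical section.
4. Identify prior diagnosis from the medical records and biopsy results that Data & Safety Monitoring already lists for analysis, naming earlier biopsies explicitly. Do not take it from the screening review, whose use is limited to eligibility.

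The cost is one line in the criteria and one sentence defining the analysis set. The recruitment pool may be slightly smaller, or fewer than 50 men may enter the benchmark comparison. For scale, the approximate 95% half-width at a 30% rate, 1.96 × √(0.30 × 0.70 / n), is 12.7 points with 50 men and 14.2 points with 40 (an assumed 20% known-cancer share).

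### The ARFI-versus-fusion comparison of cancer length and grade does not say how benign cores enter; if they drop out, it can favour the method that misses more small cancers

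*Combined protocol and SAP*

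**What the plan says.** All references are to the combined protocol and SAP, section Data Analysis & Statistical Considerations, unless stated.

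- The Part 2 hypothesis is that "ARFI guided targeted biopsy provides a higher PCa detection rate than that reported for systematic TRUS biopsy". The reference there is a published rate, and the sample size relates only to it.
- The fusion comparison follows as a further aim: "We will also compare ARFI-targeted biopsy performance to that of MR-ultrasound fusion targeting". It is to be made "by evaluating the biopsy cores obtained using each method", "with standard statistical tests to compare the length and grade of cancerous tissue in the cores". No test is named, and no value is given for a core without cancer.
- The next sentence lists the scoring items ("percent PCa per/core, Gleason score, Gleason Grade Group") and adds "yield of CSD (i.e., number of cores containing CSD/total number of cores) for each biopsy method". This last measure has all cores in its denominator.
- Under Design & Procedures, each man has ARFI-targeted cores and then the standard fusion biopsy. For ARFI, "the most suspicious targets (up to 3) in the gland will be identified" and "two-four biopsy cores will be acquired per target". The number of fusion cores is not given.

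**The concern.** A Gleason score or Grade Group exists only where a core contains cancer. Length of cancer can be set to 0 mm in a benign core, but only if the analyst decides to enter the zero, and the plan does not say so. If benign cores drop out, the comparison is between ARFI-positive and fusion-positive cores, two sets each selected by that method's own success.

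A method that finds only large lesions then keeps a sample of long, high-grade cores. A method that also finds small cancers lowers its own average. Allowing for pairing or for clustering of cores within men does not remove this, because the selection is on the outcome itself.

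Comparison with fusion is part of the aim of Part 2 in Purpose of the Study. Under Data & Safety Monitoring the data are analysed once enrolment is complete. An unwritten rule for benign cores could therefore be settled after the results are known.

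**Working it through.** The plan gives no figure for the ARFI-fusion comparison, so there is none to reproduce. The documents also give no lesion sizes, hit rates or core lengths. Every input below is assumed, and the results show direction only.

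**1. Core-level arithmetic.** Assume 100 cores per method, with 8 mm of cancer in a core that hits a large lesion and 3 mm in one that hits a small lesion. Clinically significant disease (CSD) is present in 90% and 30% of those cores. Method A hits 30 large and 30 small; method B hits 30 large and 10 small.

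| Measure | A | B | Leads |
|---|---|---|---|
| Mean length, positive cores | (30×8 + 30×3)/60 = 5.50 mm | (30×8 + 10×3)/40 = 6.75 mm | B |
| CSD share of positive cores | (27 + 9)/60 = 60% | (27 + 3)/40 = 75% | B |
| Mean length, all cores, benign = 0 | 330/100 = 3.30 mm | 270/100 = 2.70 mm | A |
| CSD yield, all cores | 36/100 = 36% | 30/100 = 30% | A |

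B finds nothing that A misses, yet it leads on both measures restricted to positive cores.

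**2. The same at the level of men.** Suppose one method is positive in 15 of 50 men with mean 6 mm, and the other in 25 of 50 with mean 5 mm. Positives only: 6 v 5 mm. With zeros kept: 15×6/50 = 1.8 mm v 25×5/50 = 2.5 mm. The order reverses.

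**3. How often a 50-man trial would be misled.** Assume 6 cores per method per man, 30% of men with no lesion, 35% with a small one and 35% with a large one. Lengths average 8 and 3 mm (SD 1.5), with the same CSD shares as in step 1. A hits large and small lesions at 0.6 and 0.5 per core; B at 0.6 and 0.2.

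Expected all-core length:
- A: 0.35×0.6×8 + 0.35×0.5×3 = 2.205 mm
- B: 0.35×0.6×8 + 0.35×0.2×3 = 1.890 mm

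Expected positive-core length:
- A: 2.205/0.385 = 5.73 mm
- B: 1.890/0.280 = 6.75 mm

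In 4,000 simulated trials, B (the poorer detector) looked better in:

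| Measure | B hits 0.6 / 0.2 | B hits 0.55 / 0.2 |
|---|---|---|
| Mean length, positive cores | 99.9% | 99.7% |
| Mean length, all cores | 7.8% | 1.8% |
| CSD yield, all cores | 12.1% | 4.2% |

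With equal methods all three are near 50%.

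**4. A different model.** Assume half of men have a lesion, with mean diameter 10 mm, and that the methods reach 50% detection at 12 and 8 mm. They then detect cancer in 17% and 30% of men. Positives-only length favours the poorer detector in 80% to 85% of trials, depending on how cancer length in a core is modelled. With zeros kept it does so in 3% to 4%. With a smaller gap (10 and 8 mm; 23% v 30% detected) the figures are about 72% and 17%.

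**5. Effect of core count on a per-man maximum.** This matters for the remedy. With independent cores and an assumed 30% hit rate, 6 cores give 1 − 0.7^6 = 88% of men positive and 3 cores give 1 − 0.7^3 = 66%. Two equally accurate methods would differ on any per-man maximum because of core count alone. ARFI may take up to 3×4 = 12 cores, and the fusion count is unknown.

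**The case against.** A reader might infer that the plan as written tests positive cores only, and so gives missed cancers no penalty anywhere. The documents do not support that, for two reasons.

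First, the text speaks of the cores obtained by each method and does not limit them to those with cancer. A benign core can be scored 0 mm, and the percentage of cancer per core, also listed, is naturally 0% there. Only grade lacks a value. For length the restriction is a possibility left open.

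Second, the CSD yield counts every core, so missed significant disease lowers it. In step 3 it put the poorer detector ahead in only 12.1% or 4.2% of trials, so a reader of the results would have a measure that usually ranks the methods correctly.

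Both points stand, but they do not close the gap. Yield has no stated test and no priority over length and grade, so the plan does not say which governs if they disagree. It covers CSD only. It is a per-core ratio, so a man whose cancer one method missed is not counted as such. No within-man detection comparison is described, although each man has both biopsies.

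It is also fair to say that the reversals rest on assumed inputs, and that the study is one of feasibility whose stated hypothesis and sample size concern systematic TRUS biopsy.

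**Conclusion.** The concern holds as an omission. The plan does not define how benign cores enter the length and grade comparison. Taken literally, the grade comparison is conditional on detection, and the length comparison is too if zeros are not entered. In that case it can favour the method that misses more small cancers.

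The direction is the same under a core-level and a lesion-size model, and it disappears when the methods are equal. The size cannot be known from the documents; the percentages above illustrate assumed inputs and do not predict this trial. The all-core CSD yield offsets the problem in part.

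This is a worthwhile, inexpensive improvement to a secondary comparison. It does not affect the hypothesis against systematic TRUS biopsy, and it is not a must-fix error.

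**What to change.** In the Part 2 paragraph of Data Analysis & Statistical Considerations, before the data are analysed, replace the length and grade wording with a rule of this kind:

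- Score every benign targeted core as 0 mm of cancer and as an ordered no-cancer grade category.
- For each man and each method, take the mean cancer length per core over all targeted cores, and the highest Grade Group (0 = none).
- Compare the two methods within man over all men in the Part 2 analysis, including those benign by both methods, for example with a Wilcoxon signed-rank test and a confidence interval. Say how zero differences are treated, and how a man with no target by one method is scored.
- Report these beside the all-core CSD yield and the number of cores per method.
- Give length and grade among positive cores descriptively only.

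Mean length per core is preferred to maximum length because a per-man maximum rises with core count (step 5). The highest Grade Group has the same weakness, so it must be read alongside the core counts.

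The cost is a few sentences and slightly more analysis work. No additional patients, cores or pathology are needed.

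### The Part 2 power statement (80/90/95% at 35/45/50 patients) is not the power of the named equivalence test or of the hypothesis of a higher detection rate, and its 70% input is mislabelled

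*Combined protocol and SAP*

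**What the plan says.** All the statistical elements stand in the Part 2 paragraph of Data Analysis & Statistical Considerations.

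- **Hypothesis:** "we will test the hypothesis that ARFI guided targeted biopsy provides a higher PCa detection rate than that reported for systematic TRUS biopsy".
- **Planning value and its support:** "Assuming an ARFI imaging specificity for CSD of 70% (our preliminary data from Protocol Pro00006458 in patients receiving radical prostatectomy yielded 79% CSD". In full, the two supporting figures are "79% CSD from ARFI suspicious regions, and, 71% detection of all CSD present in the gland".
- **Comparator:** "comparing to the systematic sampling TRUS PCa mean detection rate of 30% that has been well-established in the literature".
- **Test:** "one-mean, one-sample equivalence test with a 30% testing margin and a standard deviation of up to 20% of the target ARFI imaging specificity".
- **Result:** "inclusion of 35, 45, and 50 patients would achieve study powers of 80%, 90%, and 95%, respectively". The plan takes 50 patients and adds 10 for early development.
- **A further measure, per core:** "yield of CSD (i.e., number of cores containing CSD/total number of cores) for each biopsy method".

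No alpha or sidedness is given, and the unit of analysis for the powered comparison is not named. The population, under Selection of Subjects, differs from the one that supplied the preliminary data: "We will enroll patients with suspected PCa who are scheduled to undergo an ultrasound fusion-MR prostate biopsy".

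**The concern.** Two things do not fit together.

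**The test and the hypothesis.** An equivalence test asks whether a value is close to a reference. The hypothesis asks whether it is higher. A test of closeness to 30% favours ARFI being no different from systematic TRUS biopsy and counts against a large gain.

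**The planning value.** The share of suspicious regions that proved to be CSD (79%) is a PPV-type figure. The share of CSD that was found (71%) is a sensitivity-type figure. A specificity needs results in CSD-free tissue, and none are given. The 70% concerns CSD in men having prostatectomy, whereas the 30% is a detection rate for PCa. Quantity, disease definition and population all differ.

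At stake is the only statistical justification for the 50 patients (Subject Recruitment and Compensation otherwise ties the total of 60 to the grant). An analyst who ran the named test would not be testing the stated hypothesis. One who did not would have to choose test and endpoint after enrolment is complete, which is when the Data & Safety Monitoring section schedules the analysis.

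**Working it through.** **Inputs.** From the plan: planning value 0.70, reference 0.30, margin 0.30, n = 35/45/50. Assumptions: the margin is in percentage points; alpha is 0.05 or 0.025 one-sided. If the margin were relative it would be 0.30 × 0.70 = 0.21 or 0.30 × 0.30 = 0.09, and the assumed difference of 0.40 would still lie outside it. The SD wording, read literally, gives 0.20 × 0.70 = 0.14; read as 20 points it gives 0.20. Both are tried.

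**1. Reproducing 35/45/50 with the equivalence formula.** n = [SD × (z(1−alpha) + z(1−beta/2)) / (margin − difference)]². The denominator is 0.30 − 0.40 = −0.10, and squaring removes the sign. With alpha 0.05 and SD 0.20:

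- 80%: (1.645 + 1.282)² × 0.04/0.01 = 34.3, so 35
- 90%: (1.645 + 1.645)² × 0.04/0.01 = 43.3, so 44
- 95%: (1.645 + 1.960)² × 0.04/0.01 = 52.0 (51.98), so 52

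This is close to the stated 35/45/50, but the formula is invalid when the difference exceeds the margin. With SD 0.14 it gives 17/22/26.

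**2. Reproducing them as superiority by 30 points.** One-sample t-test of 0.70 against 0.30 + 0.30 = 0.60, SD 0.20:

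- one-sided 0.025: power 82/91/93% at 35/45/50 (80/90/95% would need 34/44/54)
- one-sided 0.05: 90/95/97%
- SD 0.14, one-sided 0.025: 98% or more at all three

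The 0.025 version with SD 0.20 is again close, but it is not an equivalence test.

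**3. Equivalence to the 70% target instead.** With zero difference, SD 0.20 and alpha 0.05, the formula in step 1 has denominator 0.30 and gives 4/5/6 patients. That does not match.

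**4. The named test taken literally, n = 50.** Probability of concluding equivalence = Φ((0.30 − d)/SE − z) − Φ((−0.30 − d)/SE + z), with SE = SD/√50 and z = 1.645.

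- True 70% (d = 0.40), SD 0.20: SE = 0.0283; first term Φ(−3.54 − 1.645) = Φ(−5.18), about 1e-7
- True 70%, SD 0.14: SE = 0.0198; Φ(−5.05 − 1.645) = Φ(−6.70), about 1e-11
- True 30% (d = 0): above 99% with either SD

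Alpha 0.025 makes the first two smaller still.

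**5. Tests that fit the hypothesis, n = 50, null 30%.** The true rates are assumptions.

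Per-patient yes/no endpoint, exact binomial. Reject at 21 or more positives (actual alpha 0.048) or at 23 or more (0.012; 22 or more gives 0.0251, just over 0.025).

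| True rate | One-sided 0.05 | One-sided 0.025 |
|---|---|---|
| 35% | 19% | 7% |
| 40% | 44% | 23% |
| 45% | 71% | 50% |
| 50% | 90% | 76% |
| 55% | 98% | 92% |
| 60% | >99% | 98% |
| 70% | >99.9% | >99.9% |

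Per-patient mean yield, one-sample t-test, SD 0.20 as an example: 54% or 41% at a true mean of 35%, and 97% or 93% at 40%. At a true 40%, then, the two endpoints give 44% against 97% at one-sided 0.05.

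**The case against.** **The numbers can be reproduced, so the power is supported.** Partly right. They come out approximately in two ways, and superiority by 30 points agrees with the direction of the hypothesis. The calculation may be sensible and 'equivalence' only a wrong label. But the plan does not say so, both matches need an SD of 0.20 where the literal wording gives 0.14, and the other match rests on a lost minus sign.

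**The 70% is not invented.** True: it sits just below both preliminary figures. The gap is the step from CSD accuracy in prostatectomy patients to PCa detection in men referred for fusion biopsy.

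**The plan speaks of a mean with an SD, so a yes/no endpoint should not be imposed.** This stands. A per-patient proportion of positive cores is at least as natural a reading, and step 5 shows how much the choice matters. Any restated power must depend on the endpoint chosen.

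**It is a feasibility study.** This stands as to weight, but the plan still states a formal hypothesis and claims 95% power.

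A reader might go further and infer that the trial is underpowered, or, from the last row of the table, that 50 patients are ample. The documents support neither. The first needs a true detection rate that they do not give, and the second treats the 70% as a detection rate, which it is not.

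**Conclusion.** The concern holds as a fault in test specification and labelling. The stated 80/90/95% is not the power of the named test, which at the plan's own inputs is effectively zero. Nor is it the power of a test of the stated hypothesis against 30%. The 70% is not a specificity on the evidence given, and it is compared with a rate for a different disease definition. These conclusions rest on a margin of 30 points, an SD of 0.14 or 0.20 and an assumed alpha; no combination of these rescues the literal test. Whether 50 patients suffice is undetermined until the endpoint, its unit and a planning rate are stated. The plan should be corrected, but the point is no objection to the patient number.

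**What to change.** Revise the Part 2 paragraph and leave the patient number unchanged.

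1. Drop the word specificity. Label 79% as PPV-type and 71% as sensitivity-type for CSD, both from prostatectomy patients.
2. Use one disease definition for hypothesis, planning rate and comparator (PCa, to match the hypothesis and the 30%). State the planning rate as an assumption for men referred for fusion biopsy.
3. Replace the equivalence test and margin with a one-sample superiority test against 30% at a stated one-sided alpha. Name the unit of analysis, and say how men with no ARFI target count: Design & Procedures allows up to three targets and sets no minimum.
4. Restate power for the endpoint chosen. If it is per-patient yes/no, use the exact binomial test and the table in step 5. If it is a per-patient mean yield, use a one-sample t-test and give the source of the SD; the SD 0.20 figures in step 5 are only an example.

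The cost is text only, with no extra patients or procedures. The downside is that the single 95% figure becomes conditional on the true rate.
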